#### **4.3 Intervention**

External beam radiation therapy will be administered on an outpatient basis, once daily (except weekends and holidays) for approximately two weeks. Patients will undergo a simulation prior to initiation of radiation. Once an IMRT plan is generated which meets all dose constraints specified in section 9.3.3, patients will be treated with 6MV photons for 10 treatments. Any pediatric patients who are too young to lay still on a daily basis will receive general anesthesia per department practice.

### **5.0 THERAPEUTIC/DIAGNOSTIC AGENTS**

IMRT is a sophisticated technique that uses a computer controlled multileaf collimator to shape the intensity of each treatment beam to optimally deliver the dose to the tumor and protect normal tissue. IMRT is being used to deliver WLI in order to minimize the dose to the heart as explained in section 3.3.2.

### **6.1 CRITERIA FOR SUBJECT ELIGIBILITY**

## 6.2 Subject Inclusion Criteria

- Patients with synovial sarcoma confirmed by MSKCC pathological review
- Patients with single or multiple lung metastases at diagnosis or that develop over the course of treatment.
- After completion of all chemotherapy, lung metastases must be  $\leq 2$  cm.
- Age  $\geq 12$  months of age
- Karnofsky performance status (KPS) must be  $\geq 70$  for patients  $\geq 16$  years of age and Lansky performance status must be  $\geq 70$  for patients  $< 16$  years of age.
- Normal cardiac function
  - No active coronary artery disease;
  - No New York Heart Association class II, III or IV disease;
  - No arrhythmia requiring treatment.
  - Baseline echocardiogram with a shortening fraction of  $\geq 27\%$  or an ejection fraction  $\geq 50\%$ .
- Female patients of childbearing potential must have a negative pregnancy test within 14 days of radiation start.
- Female patients who are lactating must agree to stop breast-feeding.
- Sexually active patients of childbearing potential must agree to use effective contraception.

## 6.3 Subject Exclusion Criteria

- Patients with a history of prior radiation therapy to the thorax.
- Patients requiring a field size  $>40$  cm as IMRT cannot be performed at extended SSDs.
- Patients with any concurrent medical or psychiatric condition or disease which, in the investigator's judgment, would make them inappropriate candidates for entry into this study.

## 7.0 RECRUITMENT PLAN with recruitment plan addendum

All patients meeting the eligibility requirements will be considered for enrollment regardless of gender, race, or religion. Patients will be made aware of the protocol, its specific aims and objectives, and the potential risks and benefits that the patient may incur. Patients will be consented by the treating radiation oncologist at MSKCC. They will be required to agree to and sign an IRB-approved informed consent form prior to registration. There will be no financial compensation for patients enrolling in this protocol.

As a comprehensive cancer center, MSKCC is in a unique position to recruit patients for this protocol as we are hoping to recruit both pediatric and adult patients and MSKCC has high-volume adult and pediatric sarcoma services. This study mirrors the national trend of including both pediatric and adult patients on sarcoma protocols. The soon to open ARST 1321-RTOG 1313 is a joint protocol sponsored by the COG and RTOG to study non-rhabdomyosarcoma soft tissue sarcoma across the age spectrum.

Potential research subjects will be identified by a member of the patient's treatment team, the protocol investigator, or research team at Memorial Sloan-Kettering Cancer Center (MSKCC). If the investigator is a member of the treatment team, s/he will screen their patient's medical records for suitable research study participants and discuss the study and their potential for enrolling in the research study. Potential subjects contacted by their treating physician will be referred to the investigator/research staff of the study.

The principal investigator may also screen the medical records of patients with whom they do not have a treatment relationship for the limited purpose of identifying patients who would be eligible to enroll in the study and to record appropriate contact information in order to approach these patients regarding the possibility of enrolling in the study.

During the initial conversation between the investigator/research staff and the patient, the patient may be asked to provide certain health information that is necessary to the recruitment and enrollment process. The investigator/research staff may also review portions of their medical records at MSKCC in order to further assess eligibility. They will use the information provided by the patient and/or medical record to confirm that the patient is eligible and to contact the patient regarding study enrollment. If the patient turns out to be ineligible for the research study, the research staff will destroy all information collected on the patient during the initial conversation and medical records review, except for any information that must be maintained for screening log purposes.

In most cases, the initial contact with the prospective subject will be conducted either by the treatment team, investigator or the research staff working in consultation with the treatment team. The recruitment process outlined presents no more than minimal risk to the privacy of the patients who are screened and minimal PHI will be maintained as part of a screening log. For these reason, we seek a limited waiver of authorization for the purposes of (1) reviewing relevant to the enrollment process; (2) conversing with patients regarding possible enrollment; (3) handling of PHI contained within those records and provided by the potential subjects; and (4) maintaining information in a screening log of patients approached (if applicable).

## **8.1 PRETREATMENT EVALUATION**

Any time prior to treatment start:

- Confirmation of pathology at MSKCC

The following are to be completed within 45 days of registration:

- History and physical exam
- Echocardiogram
- Pulmonary function tests

The following are to be completed within 30 days of registration:

- Chest CT scan with or without contrast to evaluate pulmonary metastases after completion of systemic therapy and to serve as a baseline for follow-up scans. To be done within 30 days of treatment start.
- If lung metastases are present on Chest CT and are <2 cm, FDG-PET scan to assess avidity of pulmonary metastases after completion of systemic therapy

The following is to be completed within 14 days of treatment start

- Serum pregnancy test (for women of childbearing potential)

## **9.0 TREATMENT/INTERVENTION PLAN**

### **9.1 Simulation**

These simulation procedures represent our standard simulation procedures for comprehensive radiation therapy.

9.1.1 In order to develop a conformal treatment plan, all patients will undergo a CT simulation. IV contrast is not necessary for simulation.

9.1.2 All patients will undergo simulation in the treatment position with both upper extremities extended above their head using an Alpha Cradle (Alpha Cradle, Smithers Medical Products, North Canton, OH) or slant board immobilization.

9.1.3 Patients will be scanned with 3mm slices from the level of the mandible to the pelvic brim.

9.1.4 A 4D CT will be obtained to capture motion in all phases of the respiratory cycle. A free-breathing scan will also be obtained to be used as the planning CT scan.

### **9.2 Target Volume Definitions**

These procedures generally represent our standard procedures.

9.2.1 Normal structure and treatment volume contours will be delineated on the planning CT scan.

9.2.2. The following normal structures will be contoured.

- Heart
- Liver
- Stomach
- Right kidney
- Left kidney
- Esophagus
- Thyroid
- Right and left breast (in female patients only)

9.2.3 The following target structures will be contoured

- Target volumes will be defined according to International Commission on Radiation Units and Measurements Report-50 and 62 definitions for gross tumor volume (GTV), clinical target volume (CTV), internal target volume (ITV), and planning target volume (PTV).
- The GTV will include all areas of pre-chemotherapy lung metastases.

- The CTV is the bilateral lung volume including all pleural recesses and bilateral hila.
- The ITV is defined as an expansion on the CTV to encompass the bilateral lungs on all phases of the respiratory cycle as defined by the 4DCT. Careful review of the sagittal and coronal views of the costo-diaphragmatic recesses should help determine the inferior extent of the pleural cavity and care must be taken to ensure that they are included in the ITV.
- The PTV is defined as a 1 cm expansion on the ITV in order to account for spatial uncertainties in patient positioning and treatment delivery. This 1cm expansion of the ITV should be made in all dimensions. Compared to the standard AP-PA technique using 2-D or 3-D planning, the final PTV for IMRT in this protocol will be more accurate because we are utilizing 4-D scanning and then giving a dosimetric margin of 1cm beyond the maximum lung expansion (ITV).

- **9.3 Radiation Dose, Fractionation, Energy, and Parameters**

9.3.1 The prescribed dose for all patients will be 1500cGy in 10 fractions. 6MV energy photons will be used. Multi-beam IMRT plans, utilizing dynamic multileaf collimation, will be created based on the target tissue coverage and normal tissue avoidance parameters described below. VMAT plans are also acceptable if all specified dose constraints are achieved.

9.3.2 Ninety-five percent of the PTV should receive at least 95% of the prescribed dose. The PTV used for the purposes of the DVH is the PTV as drawn by the physician minus 5mm from the skin (i.e. the buildup region) as is our departmental practice. No more than 5% of the PTV should receive more than 105% of the prescribed dose and no more than 1% of the PTV should receive more than 110% of the prescribed dose. For organs at risk (OARs): the maximum doses to the spinal cord, breast (in female patients), and liver should be <107%, <108%, and <110% respectively of the prescribed dose. For the heart:

- 1) The maximum dose should be <110%.
- 2) The planner should reduce the mean heart dose until the specified PTV coverage constraints are approached (i.e. until the planner gets close to the D95, D05, D01 PTV limits).

#### **9.4 Treatment Plan Evaluation**

The treatment plan will be evaluated by the treating physician prior to treatment to ensure that all treatment parameters have been met. Isodose curves and dose volume histograms (DVH) will be analyzed. Evaluation criteria will include.

1. Isodose curves:
  - a. The 95% isodose line must generally conform to the PTV with visually acceptable target volume coverage and visually acceptable critical structure avoidance.
2. Dose-Volume Histogram (DVH):

- a. The maximum allowed heterogeneity will be limited to less than 5% of the PTV receiving more than 105% of the prescribed dose.
- b. The DVH must include all normal structures listed in section 9.2.2
- c. PTV DVH must meet all prescription parameters.
- d. Critical structure DVH should meet constraint parameters (described in 9.3.2).

## 9.5 Radiation Therapy Daily Treatments and Quality Assurance

Patients will receive external beam treatment once a day, 5 days a week (except weekends and holidays) for 10 treatments. Any missed radiation days will be recorded and made up. Set-up error will be minimized by weekly orthogonal pair films per departmental guidelines. These films will be checked by an attending physician weekly.

## 9.6 Treatment Interruptions

In the event that a patient must miss a scheduled treatment for non-toxicity related reasons (ie: weather, sickness, family emergencies, etc), the treatment visit will be made up at the end. If the patient misses more than 3 consecutive treatments, they will be removed from the protocol and considered inevaluable.

## 10.0 EVALUATION DURING TREATMENT/INTERVENTION

	Pre-treatment	During WLI	3 mo post-WLI	6 mo post-WLI	12 mo post-WLI	18 mo post-WLI	24 mo post-WLI	Follow up years 2-5
History	x		x	x	x	x	x	
Physical	x	x (weekly)	x	x	x	x	x	
Feasible Plan Generated	x							
Weekly Setup Data		x						
CT chest	x		x	x	x	x	x	
PET scan	x (If CT chest shows mets $\leq 2$ cm)							
Echocardiogram	x			x	x		x	
PFTs	x			x			x	
TSH					x		x	
Pregnancy test	x							

(if relevant)								
Toxicity assessment	X	X (weekly)	X	X	X	X	X	
Chart review for overall survival								X

### **10.1 Evaluations During Treatment**

All patients will undergo a routine status check visit approximately weekly during treatment. The maximum RT related toxicities graded by CTCAE version 4.0 will be submitted to the Research Study Assistant at the completion of WLI.

### **10.2 Evaluations After Treatment**

Patients will have follow-up visits with physical examinations at 3 and 6 months (+/- 3 weeks) and at 12, 18, and 24 months (+/- 6 weeks) following the completion of radiation therapy. CT scans of the chest will be obtained at 3 and 6 months (+/- 3 weeks) and at 12, 18, and 24 months (+/- 6 weeks). Echocardiograms will be obtained at 6 months (+/- 3 weeks) and at 12, and 24 months (+/- 6 weeks). PFTs will be obtained at 6 months (+/- 3 weeks) and at 24 months (+/- 6 weeks). TSH levels will be obtained at 12 and 24 months (+/- 6 weeks).

In order to obtain data on overall survival, routine chart reviews will be conducted until 5 years following the completion of treatment.

### **10.3 Evaluations of Early and Late Toxicity**

The CTCAE version 4.0 scale will be used. Early toxicities are those toxicities that occur within 3 months of the completion of treatment. Late toxicities are those that occur after 3 months following the completion of treatment.

## **11.0 TOXICITIES/SIDE EFFECTS**

### **Adverse events from WLI**

#### **Likely**

- Nausea
- Emesis
- Skin erythema
- Low blood counts
- Esophagitis

#### **Less Likely**

- Thyroid dysfunction
- Pericarditis

- Cardiac dysfunction

#### **Rare but serious**

- Pneumonitis
- Increased risk of secondary cancer
- Pulmonary fibrosis

**Reproductive risks:** Treatment on this study can affect an unborn child. Patients should not become pregnant or breastfeed a baby while being treated on this study. Sexually active patients who are at risk of getting pregnant or fathering a baby must use an effective method of contraception to avoid pregnancy while on treatment and for at least 3 months thereafter.

#### **Definition of a Serious Adverse Events (SAE):**

- A Serious Adverse Event is an adverse experience that:
  - Is fatal or life-threatening
  - Is disabling
  - Results in hospitalization or prolongation of hospitalization
  - Results in a congenital anomaly or occurrence of malignancy
  - Any adverse event that is possibly related to WLI that is grade 3 or higher will be considered an adverse event.

#### **Evaluation of SAE:**

Review of the patient record including the treatment dosimetry will be undertaken by the principal investigator and investigators of the study. The principal investigator in conjunction with the investigators of the study may decide to continue the protocol without modification, discontinue the study altogether, or to modify the protocol prior to enrolling more patients pending the results of the review.

#### **Unacceptable Toxicity:**

Enrollment on the protocol will be suspended for WLI related acute toxicities  $\geq$  grade 4 radiation pneumonitis, esophagitis, pericarditis, cardiac dysfunction, and acute chest wall pain. If one of these events is observed in one patient, then the protocol will be closed to further accrual until review by the principal investigator in conjunction with the investigators of the study.

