## **12.0 CRITERIA FOR THERAPEUTIC RESPONSE/OUTCOME ASSESSMENT**

### **12.1 Assessment of Primary Objectives**

12.1.1 Assessment of the overall toxicity rate will occur at the pre-specified follow-up time-points using the CTCAE version 4.0 grading system. The radiation oncologist will score toxicity at each visit. Any toxicity recorded within three months of completion of radiation will be considered acute. Any toxicity after three months from completion of radiation will be considered late toxicity.

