### **14.0 BIOSTATISTICS**

The primary objective of this protocol is to assess the safety of whole lung IMRT following standard treatment in patients with synovial sarcoma and lung metastases. To this end we will enroll 15 eligible patients which will take about 6 years. Due to this long enrollment time the safety endpoint

will include both acute (<=3 months from the end of WLI) and late toxicities (>3 months from the end of WLI). Namely, we will evaluate the rate of any grade 3 toxicities (including pneumonitis, esophagitis, pericarditis and cardiac dysfunction) by using Kaplan-Meier estimation. If a patient withdraws from the protocol (expected to be 10% within 1 year), or dies without any grade 3 toxicities (expected to be 50% at 1 year) he/she will be regarded as a censoring at such time points. We will not use a competing risks analysis because it is expected that the withdrawal and death are independent from toxicities, and the actuarial estimate is believed to be more illustrative of the toxicity profile than the cumulative incidence rate by regarding death as a competing risk. For the decision rule we will look at the 1-year toxicity rate. If, the higher bound of the 85%, 1-sided confidence interval of the 1-year toxicity rate based on the (one minus) Kaplan-Meier estimate is lower than 0.25 than we will declare the whole lung IMRT procedure safe. This unusually high type 1 error rate, 15%, is used due to the rareness of such patients and the high progression/mortality rate without WLI. To roughly assess the power of the study with 15 patients, we simulated 10,000 datasets based on the above assumptions and examine the 1-year toxicity rate by Kaplan-Meier method. The following table shows probabilities of claiming whole lung IMRT safety under various values of the true 1-year toxicity rate.

True 1-year toxicity rate	0.05	0.10	0.15	0.20	0.25	0.30	0.35
Probability of claiming whole lung IMRT safe	0.894	0.712	0.536	0.364	0.243	0.154	0.094

As mentioned in Section 11.0, this study is also subject to early stopping if any radiation-related acute toxicities of grade 4 or higher are observed among the patients. If one of these events is observed in one patient, then the protocol will be closed to further accrual until reviewed by the principal investigator in conjunction with the investigators of the study.

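### The accrual hold covers only acute toxicity, so a late WLI-related grade 4 or 5 event must be reviewed but does not automatically pause enrolment

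*Combined protocol and SAP*

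**What the plan says.** **The hold.** Section 11.0, under Unacceptable Toxicity, says "Enrollment on the protocol will be suspended for WLI related acute toxicities" of grade 4 or higher. It names pneumonitis, esophagitis, pericarditis, cardiac dysfunction and acute chest wall pain. One event is enough: "If one of these events is observed in one patient, then the protocol will be closed to further accrual until review by the principal investigator", acting with the other investigators. Section 14.0 repeats the rule as "this study is also subject to early stopping if any radiation-related acute toxicities of grade 4 or higher are observed among the patients", with no list of toxicities.

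**Acute and late.** Section 12.1.1 says "Any toxicity recorded within three months of completion of radiation will be considered acute" and "Any toxicity after three months from completion of radiation will be considered late toxicity". Sections 10.3 and 14.0 put the boundary at the same 3 months.

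**The endpoint.** Section 14.0 gives a reason for counting both periods. It begins "Due to this long enrollment time the safety endpoint" and continues "will include both acute (<=3 months from the end of WLI) and late toxicities (>3 months from the end of WLI". The safety decision is taken on the 1-year rate.

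**Other safety provisions.**
- Section 11.0, Evaluation of SAE, requires a review of the patient record and dosimetry. After that review the investigators "may decide to continue the protocol without modification, discontinue the study altogether, or to modify the protocol prior to enrolling more patients".
- Section 11.0 counts fatal and life-threatening events as serious, with no time limit.
- Section 17.2 requires serious events to be reported to the IRB/PB within 5 calendar days.
- The Design text in section 4 says accrual is to end if toxicity exceeds what was expected. It is not limited to acute events. It states no grade, count or expected level, and it sends the reader to section 11.0 for the rules.

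**The concern.** The plan counts late toxicity in its safety endpoint because enrolment is long, but does not carry that reasoning into the rule that closes accrual. Read literally, grade 4 pneumonitis at week 11 closes enrolment until it has been reviewed, while the same event at month 4 does not.

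The plan's own background gives reasons to watch the later period. Section 11.0 lists pneumonitis and pulmonary fibrosis as rare but serious. Section 3.3.1 says many cardiac effects of radiation appear only years later. Section 3.3.3 says there are no data on pulmonary toxicity after WLI given with IMRT. Patients can be as young as 12 months.

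At stake is whether a further patient can be enrolled and irradiated while a late grade 4 or 5 event is still under review. The primary estimate is not affected, because late events count in it either way.

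**Working it through.** The plan gives no figure for the hold itself, so the check is mainly a comparison of its rules.

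| Provision | Covers late events? | Defined trigger? | Closes accrual during review? |
|---|---|---|---|
| Section 11.0, Unacceptable Toxicity | No | Yes: one listed event, grade 4 or higher | Yes |
| Section 14.0, restated hold | No | Yes: one event of any kind, grade 4 or higher | Yes |
| Section 11.0, Evaluation of SAE | Yes | Yes: any SAE | Not stated; the outcome is at the investigators' discretion |
| Section 17.2, SAE reporting | Yes | Yes: any SAE | No; notification only |
| Section 4, Design | Yes | No | Ends accrual, but refers to section 11.0 for the rule |

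No row both covers late events and closes accrual on a defined trigger.

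**Event scope.** The section 11.0 list omits pulmonary fibrosis. Section 14.0 covers any radiation-related acute event. An acute grade 4 toxicity that is off the list closes accrual under section 14.0 but not under section 11.0.

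**The boundary.** Section 10.3 classifies by when the toxicity occurs, section 12.1.1 by when it is recorded. The 3-month visit may fall 3 weeks late (section 10.2). An event that occurs before month 3 but is first recorded at such a visit is early under one section and late under the other.

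**Share of the endpoint outside the hold.**
- By time: (12 − 3)/12 = 75% of the 1-year window.
- By events, assuming a constant toxicity hazard. Let p be the true 1-year toxicity rate. Without censoring, the late share is 1 − [1 − (1 − p)^0.25]/p. This is 75% at p = 0.05 and 71% at p = 0.35.
- With section 14.0's 50% death and 10% withdrawal at 1 year, also as constant hazards: λ = −ln(1 − p), h = λ + ln 2 − ln 0.9, F(t) = (λ/h)(1 − e^(−ht)), and late share = 1 − F(0.25)/F(1). At p = 0.25: λ = 0.288, h = 1.086, F(0.25) = 0.063, F(1) = 0.1755, so the share is 64%. The range is 67% (p = 0.05) to 63% (p = 0.35).

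The same exponential assumptions, with a log-transformed confidence bound, reproduce section 14.0's probabilities of a safe claim: 0.884 / 0.707 / 0.529 / 0.366 / 0.247 / 0.161 / 0.097 against the stated 0.894 / 0.712 / 0.536 / 0.364 / 0.243 / 0.154 / 0.094. The largest gap is 0.010. The shares refer to the toxicity endpoint as a whole. The documents give no separate timing for grade 4 or 5 events.

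**Chance that the gap matters in this trial.** The plan gives no rate q of late grade 4 or higher WLI-related events per patient. Over an assumed range, P(at least one in 15) = 1 − (1 − q)^15:

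| Assumed q | 1% | 2% | 5% | 10% |
|---|---|---|---|---|
| At least one late event | 14% | 26% | 54% | 79% |

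**Exposure per event.** Accrual is 15/6 = 2.5 patients per year, or one per 365/2.5 = 146 days. The hold lasts only until the review is done, so what matters is entries between event and review:
- 5 days (the reporting limit): 5/146 = 0.03 patients.
- 30 days (an assumption; the plan sets no review time): 30/146 = 0.2 patients. Each further 30 days adds 0.2.

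**The case against.** The strongest reply is that a late death is not ignored. Section 11.0 says the SAE review is to be undertaken; only its outcome is discretionary, and changing the protocol before more patients enter is among the options. Reporting within 5 calendar days is compulsory. Section 16.2 adds institutional monitoring. The people who would lift the hold are the same investigators who carry out the SAE review. All of this stands. A reader might infer that nobody is required to review a late WLI-related death, and the documents do not support that.

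A reader might also measure the exposure by everyone entering during a patient's months 3 to 12: 9 months at one per 4.8 months (72/15), or 1.9 patients. That is the wrong measure, because a hold would end with the review, not at month 12.

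Nor do the documents support saying that 12 to 13 patients (15 × 5/6 = 12.5) would be observed for a full year while accrual is open. With the plan's 50% death and 10% withdrawal, taken as independent, about 12.5 × 0.5 × 0.9 = 5.6 would still be under observation at 1 year, before allowing for toxicity.

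Section 4 uses mandatory wording that is not limited to acute events, so the acute hold cannot be called the only mandatory stopping provision. It is the only one with a defined trigger.

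Finally, section 3.3.3 is reassuring overall. In the study with abnormal lung function at 6 and 12 months, the abnormalities resolved by 2 years without significant symptoms, and the section concludes that clinically significant toxicity is uncommon at 15 Gy. That lowers the likely frequency of late severe events but does not explain why the rule should differ before and after month 3.

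**Conclusion.** The point holds in a limited form. As written, a WLI-related grade 4 or 5 event after month 3 must be reviewed and reported, but accrual does not close automatically while that review runs. The same event before month 3 would close it if it is on section 11.0's list, or whatever its kind under section 14.0. The gap covers 9 of the 12 months on which safety is judged. The two statements of the hold also conflict on which acute events trigger it.

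The practical size is small: about 0.03 patients entering in 5 days, or 0.2 in an assumed 30-day review, at even accrual of 2.5 per year. The documents do not show that enrolment would in fact continue after a late death, since the investigators may stop or modify the study at any time. The finding about the rule rests on the text alone. The late-event shares rest on a constant hazard, and the chance of at least one late event rests on assumed rates. This is a cheap improvement to patient protection and internal consistency, not a flaw in the primary analysis.

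**What to change.** Reconcile the Design text in section 4, the Evaluation of SAE and Unacceptable Toxicity paragraphs in section 11.0, and section 14.0, so that:

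- the existing accrual hold pending investigator review has one event scope, stated identically in sections 11.0 and 14.0, with the place of pulmonary fibrosis made explicit;
- the hold also covers late WLI-related events within the safety endpoint;
- section 4 points to that rule;
- sections 10.3 and 12.1.1 use one basis, occurrence or recording, for the 3-month boundary.

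The review process stays as it is. Deleting the word acute in both sections would not be enough: the list and the any-event wording would still conflict, fibrosis would remain off the list, and the word also belongs to the name of one listed toxicity. Which events belong in the scope is for the investigators to settle.

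The cost is a short text amendment and an occasional brief pause in a trial that enrols about 2.5 patients per year. Sample size, endpoint and analysis are unchanged.
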